A billable service is defined as any service rendered to a study subject that, if he/she was not on a study, would normally generate a bill from either Yale-New Haven Hospital or Yale Medical Group to the patient or the patient's insurer. The service may or may not be performed by the research staff on your study, but may be provided by professionals within either Yale-New Haven Hospital or Yale Medical Group (examples include x-rays, MRIs, CT scans, specimens sent to central labs, or specimens sent to pathology). Notes: 1. There is no distinction made whether the service is paid for by the subject or their insurance (Standard of Care) or by the study's funding mechanism (Research Sponsored). 2. This generally includes new services or orders placed in EPIC for research subjects.

If answered, "yes", this study will need to be set up in OnCore, Yale's clinical research management system, for Epic to appropriately route research related charges. Please contact [contact]

Are there any procedures involved in this protocol that will be performed at YNHH or one of its affiliated entities?

Yes **No**

IMPORTANT REMINDER ABOUT RESEARCH AT YNHH

Please note that if this protocol includes Yale-New Haven Hospital patients, including patients at the HRU, the Principal Investigator and any co-investigators who are physicians or mid-level practitioners (includes PAs, APRNs, psychologists and speech pathologists) who may have direct patient contact with patients on YNHH premises must have medical staff appointment and appropriate clinical privileges at YNHH. If you are uncertain whether the study personnel meet the criteria, please telephone the Physician Services Department at [contact]. **By submitting this protocol as a PI, you attest that you and any co-investigator who may have patient contact has a medical staff appointment and appropriate clinical privileges at YNHH.**

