Home testing is a promising approach to increase testing and linkage to care for HIV because it can reach individuals outside the health system, eliminate the costs of traveling for testing, offer testing in a familiar environment, and increase engagement with care among those found to be living with HIV. Nevertheless, many individuals offered home HIV testing in sub-Saharan Africa decline to test. Our group has previously shown that social interactions at the time HIV testing is offered strongly influence perceived stigma and test uptake. When potential testers discern that others have declined, they say they fear that testing will be socially discrediting. In adjusted analyses, individuals were 4 times as likely to decline testing when the first member of their home declined testing as when that individual accepted.

Nearly a century of research demonstrates that observations of peers' choices profoundly influence perceptions, judgments, and subsequent behaviors. Moreover, status and social ties among group members modify their influences on one another. The scientific premise of this proposal is that we can apply established principles from social and behavioral science to facilitate interactions within the household that reduce perceived stigma and promote uptake of HIV testing. Specifically, we will design an intervention that 1) optimizes the order of test invitations to establish testing as the normative choice; 2) frames testing as a prosocial behavior that promotes household well-being; and 3) maximizes acceptability by offering oral testing. We hypothesize that offering and delivering HIV testing in ways that reduce perceived stigma will ultimately have strong effects on the proportion of patients completing HIV testing and linking to care.

Together with our partners in Uganda, we propose to develop and pilot a complex intervention to increase uptake of home HIV testing and linkage to HIV care among household members offered home-based HIV testing. We aim:

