Aim 1: To develop a complex intervention to increase uptake of testing for HIV among household members by reducing perceptions of stigma associated with HIV and testing for HIV. Lay health workers (LHWs) will deliver a novel invitation strategy for HIV testing in 20 purposively sampled households that includes 1) acceptance-optimized sequencing, 2) prosocial messaging, and 3) salivary HIV testing. We will administer HIV and TB stigma scales before and after the invitation. We will interview all household members following the visit and engage LHWs in focus group discussions to explore feasibility and acceptability of the invitation strategy. We will iteratively refine the intervention to optimize acceptability and reductions in perceived stigma, for evaluation in Aim 2.

Aim 2: To evaluate the intervention on household HIV stigma and uptake of testing among household members undergoing TB contact investigation in a household-randomized pilot trial. We will recruit a prospective cohort of multiple-contact households undergoing routine contact investigation for TB. Households will be randomized to one of two study arms. Households in the control arm will receive routine household contact investigation services, including free, optional oral HIV testing. Households in the intervention arm will receive routine household contact investigation services and free, optional oral HIV testing with the social-behavioral framing intervention. LHWs in the intervention arm will use acceptance-optimized sequencing of invitations and a prosocial invitation script to offer salivary testing for HIV to household members. We will measure our co-primary outcomes of HIV and TB stigma using standardized instruments before invitation and after completion of post-test counseling. We will measure the proportion consenting to HIV testing, yield of HIV diagnoses, and the proportion of new PLWH linked to HIV care at 1 month and reassess household HIV and TB stigma at 3 months in a subset of participating households. Participants may also be contacted at a later point for interviews, focus-group discussions or surveys to better understand the implementation and impact of the intervention.

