Layered stigma is associated with worse outcomes than HIV stigma alone. Stigma is best understood as a dynamic social process rather than an individual attribute.^{27,28} When stigma is layered, social devaluation from two socially discrediting conditions can operate synergistically. Households undergoing TB contact investigation face or anticipate facing at least two stigmatized conditions, HIV and TB. TB-HIV stigma has consequences for TB care-seeking, TB-HIV outcomes, and HIV management.²⁹

Uganda provides a representative setting for expanding and improving home HIV testing by reducing household stigma for HIV & TB. Uganda is a high HIV-TB-burden country, with estimated HIV prevalence of 7.1% and TB prevalence of 253 per 100,000. More than 25% of PLWH are unaware of their HIV status.³⁰ Uptake of door-to-door home HIV testing ranges from 69%–95%^{7,8,13}, but uptake of HIV testing among household contacts of TB patients is only 53%.²⁰ The PLWH Stigma Index found that >60% of Ugandan PLWH experienced malicious gossip in their family or community in the past year and nearly 10% had been excluded from family activities.³¹ TB stigma may be even more common in Uganda; nearly 50% of survey respondents hold stigmatizing attitudes toward TB, compared to 26% with stigmatizing attitudes toward HIV.³²

There is a need to build awareness of and capacity for integrating stigma hypotheses and measures into research on HIV-TB in Uganda. We propose two specific capacity-building initiatives that will draw on experiences building capacity for mixed-methods and implementation research through our Fogarty D43 Pulmonary Complications of AIDS Research Training program. First, we will sponsor a doctoral student from Makerere University to work on this project. Second, each year, we will sponsor a symposium highlighting current research and future priorities in HIV and TB stigma at the Makerere Joint Annual Science and Health Conference at Makerere University, and include patients, families, researchers, and program officials.

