Randomization: For aim 2 of the study, variable block randomization will be done at the level of the household and will be performed at the time of household enrollment. Block sizes will have a minimum of 2, a maximum of 6. We will utilize study randomizer, an online randomization tool with concealed randomization. When a CHW has deemed an index patient and their household to be eligible for the study, and after the index patient or their guardian has provided verbal informed consent, the CHW will place a phone call to the study coordinator. The study coordinator will then enroll the household using the study randomizer tool and let the CHW know the study allocation. The CHW will then fill in the appropriate allocation, along with the randomization ID, and contact the appropriate CHW team for the household visit.

Households randomized to intervention group will be offered oral testing with the social-behavioral intervention. Households randomized to the standard of care group will be offered oral testing without any social-behavioral intervention. CHWs will operate in teams that are always assigned to the same arm of the study. There will be three teams of CHWs in total: one intervention group, one standard of care group, and one clinic-based group that will always be in charge of initial enrollment of index patients and recording any clinic follow up by individuals in either arm of the study.

Integrated intervention. In Intervention Households only, the CHW will present the opportunity to test using the script and procedures described in the next section (“Specification of intervention components”). This script communicates that the individual is completely free to opt out of testing, but that testing is the norm. We will use “Opt-Out” testing language along with language letting them know that they can decline.

If the household contact decides to opt out of HIV testing, the CHW will carry out a survey. These questions will take approximately the same amount of time as HIV testing and counselling procedures (~20 to 30 minutes) in order to blind other household members from the testing decision of that household contact. Contact decisions to test or not to test as well as test results will be recorded in CommCare.

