1. The test statistic is the effect regression coefficient from a mixed-effects logistic regression model
2. Alpha = 0.05
3. Power = 90%
4. The proportion consenting to testing in the control group will be 0.85
5. The proportion consenting to testing in the intervention group will be 0.98 (a difference of +0.13 vs the control group).
6. An average of two household contacts will be eligible for HIV testing per household. The intra-class correlation (ICC) will be 0.59.

The total number of households needed is sensitive to the mean cluster size. Under the preceding assumptions, the necessary number of households may range from 152 if the mean number of eligible contacts per households is 2 to 138 if the mean number of contacts per household is 3. The total

number of households needed is also sensitive to the ICC. Sample size estimates assuming a range of possible ICC values, ranging from the value observed during the preliminary research (0.59) to higher values (0.65, 0.70), are not presented here although considered by the study team. Finally, the total number of households needed is sensitive to the baseline (control group) proportion of tests accepted. Sample size estimates assuming three possible baseline testing rates (75%, 80%, and 85%) in control group households have been considered. We will plan an interim blinded power analysis by an external biostatistician to readjust sample size targets as necessary for actual mean cluster size and ICC after enrolling the first 100 households.

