Analysis. In the Aim 2 analysis, our primary outcome is change in perceived HIV-TB stigma after following the first household contact tracing visit; the secondary outcome is uptake of HIV testing; we will descriptively assess linkage to care from both baseline data and intervention households. We will calculate descriptive statistics for participant characteristics, and test associations between characteristics and perceived/attributed household stigma. To test the hypothesis that invitation scripts that apply acceptance-optimized sequencing of oral test offers and prosocial messaging can decrease HIV stigma within households, we will evaluate change in HIV-TB stigma using cluster-adjusted dependent t-tests and fitting multilevel models with clustered standard errors. To test the hypothesis that prosocial messaging and theory-informed sequencing of HIV test offers can increase test uptake, we will compare testing uptake among the intervention households and pre-implementation households using cluster-adjusted chi-squared tests of proportion and by fitting multilevel logistic regression models. All hypothesis tests will be carried out at alpha of 0.05, corrected for multiple tests as appropriate. We will report household ICC for stigma as well as test uptake.

5. Genetic Testing N/A

6. **Subject Population:** Provide a detailed description of the types of human subjects who will be recruited into this study.

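### The planned description of linkage to care leaves out the randomised control arm, and its only named figure is a percentage of newly diagnosed people, a group the intervention is meant to enlarge

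*Combined protocol and SAP*

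**What the plan says.** All references are to the combined protocol and SAP.

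- **Section I item 1, Statement of Purpose.** The overall goal is to "increase uptake of home HIV testing and linkage to HIV care among household members offered home-based HIV testing". Aim 2 then lists three steps of the testing cascade in one sentence. The first two are "We will measure the proportion consenting to HIV testing, yield of HIV diagnoses"; the third is "the proportion of new PLWH linked to HIV care at 1 month".
- **Section I item 4, Analysis paragraph for Aim 2.** Change in stigma is primary and testing uptake is secondary. On linkage the plan says: "we will descriptively assess linkage to care from both baseline data and intervention households". The same paragraph compares uptake with households seen before implementation.
- **Section I item 13, Statistical Considerations.** Uptake is compared between intervention and control households by intention to treat. Linkage is not mentioned.
- **Section I item 4, Randomization.** The clinic-based team has the task of "recording any clinic follow up by individuals in either arm of the study". The referral protocol in the same item applies to both arms.

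**The concern.** There are two separate points.

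**Comparator.** The trial randomises households, yet the linkage sentence pairs the intervention arm with baseline data. Followed literally, it yields a non-randomised description while the randomised comparison goes unreported. The documents do not say what the baseline data on linkage would be. The routine register data described under Routine data collection cover contact investigation and testing uptake at 4 TB units, whereas the trial recruits through 2.

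**Denominator.** A contact counts as newly diagnosed only after accepting a test and testing positive. That happens after randomisation and is what the intervention is designed to change, so the percentage linked describes differently composed groups in the two arms. The Background (Section I item 3) reports that stigma goes with both lower uptake of testing and lower likelihood of starting treatment after diagnosis. It is therefore plausible, though not shown, that people brought in by the intervention link less often than those who would have tested anyway. The stated goal concerns household members offered testing, and the pilot is meant to inform a later randomised study, so a linkage percentage read without its context could mislead the planning of that study.

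**Working it through.** **Inputs from the documents**

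- Sample Size, Section I item 4: "The proportion consenting to testing in the control group will be 0.85"; "The proportion consenting to testing in the intervention group will be 0.98"; alpha 0.05; power 90%; 2 eligible contacts per household; ICC 0.59; about 304 contacts allocated 1:1, so 152 per arm.
- Background, Section I item 3: national HIV prevalence 7.1%; "More than 25% of PLWH are unaware of their HIV status".
- Linkage rate: none given. L (linkage among people who would test anyway) and q (linkage among added testers) are assumptions, shown over a range.

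**1. The plan's own figure.** It concerns uptake, since no sample size is stated for linkage. For a two-sided test with pooled variance:

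n per arm = [1.96 × √(2 × 0.915 × 0.085) + 1.2816 × √(0.85 × 0.15 + 0.98 × 0.02)]² / 0.13² = 94.6, so 95 contacts.

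The design effect is 1 + (2 − 1) × 0.59 = 1.59. Households per arm: 95 × 1.59 / 2 = 75.5, so 76, or 152 in total. This matches the plan. The trial is sized for uptake, and 0.85, 0.98 and 152 contacts per arm are the right inputs below.

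**2. Who enters the denominator.** If HIV risk is the same in willing and added testers, 13/98 = 13.3% of new diagnoses in the intervention arm would be people who would not have tested under control.

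**3. Effect on the percentage linked.** Suppose the intervention does not itself change linkage.

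- Control: L.
- Intervention: (0.85L + 0.13q) / 0.98.
- Difference: (0.13/0.98)(q − L) = 0.133(q − L).
- People linked per 1,000 undiagnosed and offered testing: 850L against 850L + 130q.

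With L = 0.80 and q = 0.40, the percentage goes from 80.0% to (0.680 + 0.052)/0.98 = 74.7%, a fall of 5.3 points. The number linked goes from 680 to 732 per 1,000, a rise of 52.

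Over L from 0.70 to 0.90 and q from 0.20 to 0.60, the percentage falls by 1.3 to 9.3 points and the number linked rises by 26 to 78 per 1,000. The two figures move in opposite directions whenever q lies above zero and below L. At q = L the percentage does not move.

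**4. If the intervention also improves linkage.** With q = 0.40, the apparent fall disappears once linkage among people who would test anyway rises from 80% to (0.784 − 0.052)/0.85 = 86.1%.

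**5. All eligible contacts as the denominator.** With L = 0.80 and q = 0.40, contacts newly diagnosed and linked are 0.071 × 0.680 = 4.8% against 0.071 × 0.732 = 5.2% if undiagnosed prevalence is 7.1%. They are 1.2% against 1.3% if it is 1.8% (0.25 × 7.1%). This measure moves in the same direction as the number reaching care.

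**6. Precision.** Expected new diagnoses per arm:

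- at 1.8%: 152 × 0.85 × 0.018 = 2.3 and 152 × 0.98 × 0.018 = 2.7;
- at 7.1%: 152 × 0.85 × 0.071 = 9.2 and 152 × 0.98 × 0.071 = 10.6.

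Exact 95% intervals are 9% to 99% for 2 of 3 linked, and 48% to 98% for 9 of 11.

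**The case against.** The strongest reply is that the plan already measures the whole cascade. Yield of diagnoses stands in the same sentence as linkage, so the number linked can be rebuilt as yield times the proportion linked, and a lower percentage beside a higher yield would be visible. This stands, and it limits the denominator point to how the result is reported. No section, however, says that the rebuilt figure will be presented.

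Second, linkage is descriptive. It has no hypothesis test, power claim or decision rule, so there is no planned causal contrast to bias. This also stands. A reader might infer that a planned test is compromised; the documents plan none.

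Third, the reversal depends on assumed linkage rates and on no effect of the intervention on linkage itself, whereas the protocol expects reduced stigma to ease later steps of care. This is right, and step 4 shows how such an effect would offset the fall.

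Fourth, a between-arm difference will be imprecise too. With q = 0.40, the added testers contribute only 152 × 0.13 × 0.40 × 0.018 = 0.14 to 152 × 0.13 × 0.40 × 0.071 = 0.56 linked people per arm. The gain is a measure with the right denominator and comparator, without any gain in power.

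Finally, the comparator wording may be left over from a before-and-after design, since the same paragraph also names an earlier comparator for uptake. That is plausible. But item 13 corrects the comparator for uptake only, and nothing corrects it for linkage.

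**Conclusion.** The comparator point holds on the text alone: the only analysis sentence on linkage omits the randomised control arm, although follow-up is recorded there. The denominator point holds as a caution. The one linkage figure named is conditional on a group formed after randomisation, and read alone it could fall while more people reach care. Under the assumed rates the fall is 1.3 to 9.3 points, against 26 to 78 more people linked per 1,000 undiagnosed. This rests on added testers linking less often, equal HIV risk in willing and added testers, and no effect of the intervention on linkage.

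A reader might go further and conclude that the linkage result will point the wrong way, or that the plan cannot show how many people reached care. The documents support neither: they give no linkage rate, and yield and follow-up are both collected. Nor is 9 to 11 new diagnoses per arm a ceiling. The 7.1% is a national prevalence, and the protocol describes these households as high-risk, so the true number may differ. The matter is a modest one of reporting in a pilot, but worth correcting because these data are meant to inform the next trial.

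**What to change.** 1. In the Aim 2 Analysis paragraph, make the intervention and control households the two groups for linkage, in line with the Randomization text and item 13.
2. Report descriptively, by randomised arm, the number of contacts newly diagnosed and linked by 1 month over all eligible contacts (aged 15 or over) in randomised households. Give the between-arm difference with an interval that allows for household clustering.
3. Keep the percentage of newly diagnosed people linked as a labelled descriptive step of the cascade, shown beside yield, with numerator, denominator and exact interval.

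This costs a few sentences in the Statement of Purpose and the Analysis paragraph, and no new data. The drawback is small counts: about 2 to 3 new diagnoses per arm at 1.8% undiagnosed prevalence and about 9 to 11 at 7.1%. Intervals will be wide, and the text should say that the figures are descriptive only.
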